the effects of VLNC are influenced by the concurrent availability of e-cigs varying in **nicotine concentration and flavors**. These procedures involve a sampling phase, in which the participant samples and rates the two options, followed by choice (preference) phase, consisting of a series of discrete trials in which the participant can choose between the two options (or choose to forgo either option). The option that is chosen more often is considered to have greater relative reinforcing efficacy (Comer et al., 2008). In addition to having strong internal and predictive validity (Carter et al., 2009), choice procedures have ecological validity as they mimic situations in which smokers choose which product to buy or use among those concurrently available in the natural environment. We considered a free-access procedure in which both options are made concurrently available and *ad libitum* consumption is measured, however choice procedures are generally more sensitive than free access procedures to differences among reinforcers (e.g., Griffiths et al., 1986; Shahan et al., 1999). Participants will complete **six sessions**, including the **Screening/Baseline (BL)** session, during which eligibility will be confirmed and background questionnaires will be completed. Participants will then complete five lab sessions, a minimum of 48 hours apart; each session will follow overnight smoking abstinence.

In **Lab Session 1**, only combusted cigarettes (either NNC or VLNC) will be available. This session will always occur first because, conceptually, the no-e-cig session is the baseline condition in this study; scheduling this session first ensures that smoking choices in this condition will not be affected by any potential carryover effects of e-cig exposure on smoking choices. During the sampling phase of the choice procedure ("Preference Task"), participants will sample and then rate the cigarette using the Product Rating forms. In the preference phase, participants will be prompted via computerized instructions to make a series of 10 choices. Each choice will be to either take 2 cigarette puffs or to abstain from puffing; a total of 20 cigarette puffs is available. After completing the choice task, participants will practice using the vaping devices and sample the e-liquid flavors available. They will select which cigarette and non-cigarette flavored e-liquids they want to use during Sessions 2-5.

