If the participant has indicated a current plan to commit suicide, but the LMP/study clinician has determined that immediate action is not required (no means or intent to carry out the plan) the LMP/study clinician will call them the next day to check on how they are feeling and provide them with the contact number for the Samaritans.

If the LMP/study clinician indicates that immediate action is required, let them know that the LM/clinician has their very best interest in mind and that also this situation requires that we contact the appropriate personnel in order to help protect their well-being. **Call 911** to inform emergency personnel of the situation at the most appropriate time, either while still in the presence of the participant or immediately after you leave them.

- If the participant reports current intent to commit suicide, contact the participants' parent or guardian on file (if a minor) AFTER calling 911.

Inclusion Criteria:

- 1) Ages 15-20
- 2) Daily or near daily smokers for 3 months or more
- 3) Must have used an electronic nicotine device on a minimum of two lifetime occasions.
- 4) Breath CO levels > 5 ppm (if ≤ 5 ppm, then NicAlert Strip = ≥ 3) or positive result on a comparable cotinine test (NicConfirm or IDTC Rapid Nicotine)
- 5) Speak, comprehend, and read English well enough to complete study procedures

Exclusion Criteria:

- 1) Unwilling to use research cigarettes or vaping device as part of the study
- 2) Intention to quit smoking in the next 30 days

- 3) Using tobacco products (other than cigarettes, vaping devices, or roll-your-own tobacco) ≥ 15 days in the past 30 days.
- 4) Any medical or psychiatric condition in which participation is likely to pose a significant threat to health or for which the condition could interfere with the ability of the participant to fully participate (as determined by the LMP)
- 5) Self-reported illicit use of any drug except marijuana ≥ 10 days in the past 30 days
- 6) Binge drinking alcohol (≥ 10 days in the past 30 days, $\geq 4/5$ drinks in a 2-hour period (female/male))
- 7) Pregnant or breastfeeding
- 8) CO reading > 80 ppm
- 9) Systolic BP outside the range of 90-159, diastolic BP outside the range of 50-99, or heart rate outside the range of 45-104. Participants failing for any of these criteria will be allowed to re-screen once per criterion.

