At the end of Lab Session 1, participants will be presented with the vaping device and oriented on how it will be used during Lab Sessions 2-5. The participant will watch an instructional video on how to use the device and then the RA will show the participant how to operate the device. Next, participants will be instructed how to puff (start and stop) when signaled by the computer. For this vaping practice, participants will use a flavorless e-liquid with 0 mg/ml nicotine. Participants will not be further instructed regarding puffing unless their initial puffs fail to activate the device, in which case they will be instructed to puff harder (Vansickel et al., 2012).

Sampling e-cigarette flavors

After completing the vaping practice, participants will sample the e-liquid flavors. Vaping devices containing e-liquids with 0 mg/ml nicotine in the cigarette and non-cigarette flavors will be sampled. Participants will take a few puffs from each e-liquid flavor and then will select one flavor from the cigarette-flavor category and one flavor the non-cigarette flavor category to use in subsequent sessions. The nicotine concentration of the e-liquid used in this session (0 mg/ml) differs from those used in future sessions to avoid affecting choices during future session.

Researchers will complete the End of Visit Evaluation Form, which will be entered into REDCap.

Lab Sessions 2-4 Procedures

Lab Sessions 2-4 should be scheduled at a minimum interval of 48 hours apart and ideally no more than one week later. Every attempt will be made to schedule participants at approximately the same time of day as Lab Session 1 (\pm 2 hours). If participants are not able to attend within the ideal scheduling window, the session will be scheduled on the next available day outside the ideal scheduling window. If a longer interval is needed between sessions, the RA will contact the PI or Project Coordinator for approval. All sessions will be scheduled consecutively and no session will be skipped unless otherwise informed by the PI or project coordinator. Participants will arrive at each session having abstained from smoking sufficiently to achieve a breath CO level that is \leq 5 ppm or \leq 50% below the CO level obtained at screening/baseline.

Physiological measures collected, recorded on paper, and entered into REDCap by the interviewer at the end of the visit:

- 1) CO
- 2) Blood Pressure
- 3) Heart Rate
- 4) Urine pregnancy test, if applicable

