3.1. Randomization

Randomization will be done in two stages. In the first stage, each individual will be randomized in a 1:1 ratio to either the normal nicotine content (NNC) or the very low nicotine content (VLNC) cigarettes in a double blinded fashion. The randomization will be stratified by gender, menthol status and cigarettes per day (<9, 9+). The goal is 60 subjects per cigarette group. The second randomization stage will be done within the subjects. Individuals in the two cigarette groups will be assigned to all four combinations of sessions involving e-cigs (flavor and nicotine content each at 2 levels) in counter balanced order, which provides 24 possible orders for the four e-cig sessions. The no e-cig session will always be first followed by the e-cig sessions, in an order randomly chosen from one of the 24 possible orders without replacement. Once all 24 session orders have been exhausted, the process will start over with another set of 24 orders. Each cigarette group (n=60) will end up with the same arrangement of the four sessions occurring 2 to 3 times. This will not allow for the evaluation of an order effect in the data analysis, but it will prevent a systematic bias due to the arrangement of the sessions.

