6.1. General Approach

The primary objective of this trial is to compare the effects of VLNC and NNC cigarettes, and of the availability and characteristics of e-cigs, on preference for cigarette puffs, e-cig puffs, or puffing abstinence. The within subject factors (between sessions) will allow for the comparison of two levels of nicotine concentration in e-cigs and two categories of e-cig flavors in a 2 x 2 factorial design. Statistical analyses will be performed using SAS or R. All analyses will be completed using the intent-to-treat principle unless otherwise noted. Methods for handling missing data will be specified below. All statistical tests will be two-tailed and a p-value less than 0.05 will be considered significant for all endpoints.

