6.3.1. Primary Analysis

Descriptive statistics will summarize the number of cigarette puffs by cigarette group and by session. Results will be presented in tabular and graphical format. The primary statistical model will be a linear mixed model (2) carried out according to the 2 x 2 x 2 design, where the between-subject factor is NNC or VLNC cigarettes and the two within-subject factors relate to e-cig flavor (cigarette or non-cigarette flavors) and nicotine content (very low or moderate). The session where no e-cigs are included will be analyzed separately by comparing the normal and reduced nicotine cigarettes groups using linear regression adjusting for baseline CPD from TLFB to improve precision. Sandwich standard

errors will be used to account for potential heteroscedasticity. Data from the four sessions where e-cigs are available will be analyzed using a linear mixed model to account for potential correlation between repeated measures on an individual. The mixed model for the balanced factorial design will allow for the evaluation of the three main effects and their interactions. The major concern for this approach is the occurrence of non-constant variance for the number of cigarette puffs. Therefore, sensitivity analysis will be performed to evaluate the robustness of our assumptions. A generalized estimating equation (GEE) model uses sandwich estimators and thus is less affected by unequal variances, however, is more negatively impacted by the occurrence of missing observations. Additionally, a negative binomial regression approach will check if modeling the number of puffs as count variables provides a better fit to the data. The first mixed model will assume that participant characteristics are balanced between groups due to randomization and include only the three main effects and their interactions along with the stratification variables (gender, menthol status, and CPD [continuous, from the BL TLFB]) and the number of cigarette puffs from session 1 to increase precision.

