6.4. Secondary Endpoint Analysis

Secondary endpoints will be summarized by cigarette group and lab session using the mean and standard deviation. Number of puffs of e-cigs taken are measured in sessions 2 to 5, where e-cigs are available. CO boost (i.e., post-choice CO minus pre-choice CO) is measured at every session (1 to 5). The analysis of the secondary endpoints will be a linear mixed model following the same 2 x 2 x 2 factorial design outlined in section 6.3.1. First with only main effects and interaction terms along with the stratification and the baseline values to increase precision, and then a second model adding in any important baseline characteristics as potential moderators of study outcomes.

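### Session position (2 to 5) can be estimated but is left out of the mixed models, so any common drift widens the standard errors of the e-cig contrasts to no purpose

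*Combined protocol and SAP*

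**What the plan says.** SAP 3.1 fixes session 1 (no e-cig) as the first session. The four e-cig conditions then fill sessions 2 to 5 in an order drawn without replacement from the 24 possible orders, with a fresh set once one is used up. With 60 people per cigarette group, each order occurs two or three times. On what this means for the analysis it says: "This will not allow for the evaluation of an order effect in the data analysis, but it will prevent a systematic bias".

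SAP 6.3.1 analyzes the four e-cig sessions with a linear mixed model. The first model is to "include only the three main effects and their interactions along with the stratification variables" (gender, menthol status, baseline cigarettes per day), plus "the number of cigarette puffs from session 1 to increase precision". SAP 6.4 carries the same factorial model to e-cig puffs and CO boost: "First with only main effects and interaction terms along with the stratification and the baseline values to increase precision".

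Session is a grouping for descriptive summaries only. Session position is named in no model, including the GEE and negative binomial sensitivity analyses.

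Three protocol statements bear on drift and carryover. Under Overall Study Design, lab sessions are "a minimum of 48 hours apart; each session will follow overnight smoking abstinence". Under Inclusion Criteria: "Must have used an electronic nicotine device on a minimum of two lifetime occasions". Under Vaping Device Practice, at the end of session 1, "participants will use a flavorless e-liquid with 0 mg/ml nicotine".

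**The concern.** Sessions 2 to 5 form a four-period crossover, and the usual analysis of such a design includes the period. The sentence in 3.1 appears to rule that out by treating order as something that cannot be studied. Two different quantities are involved. The effect of a whole sequence has 24 levels with two or three people each per group and cannot usefully be estimated. The effect of session position has four levels and 3 degrees of freedom, and it is close to orthogonal to e-cig condition by design.

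If puffing changes over sessions 2 to 5 in a way shared by participants, a model without position leaves that change in the within-person residual. That residual is the yardstick for the e-cig nicotine effect, the flavor effect and every interaction involving them. The covariates that 6.3.1 adds for precision cannot help here, because gender, menthol status, baseline cigarettes per day and session 1 puffs are all constant within a person over these sessions. They can sharpen VLNC versus NNC but not the e-cig contrasts.

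Some drift is plausible, since people with as few as two vaping occasions may enter, although the practice in session 1 reduces it. At stake is power for the within-subject effects on the primary endpoint.

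**Working it through.** **Inputs from the documents.** 60 completers per cigarette group, 120 in total (SAP 3.2); 24 orders in sets without replacement (3.1); two-sided 0.05 (6.1); within-subject effect size 0.5 with power of at least 97% (3.2). **Assumed, because the documents do not give them:** a within-person residual SD of 3, 4 or 5 puffs, and a linear drift of s puffs per session common to all participants.

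**The plan's own figure.** A paired t-test with effect size 0.5 and n = 60 has power 96.8% (97.2% by the normal approximation). With all 120 it is 99.97%. The stated minimum of 97% is therefore reproduced.

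**Estimability.** There are 120 × 3 = 360 within-person degrees of freedom. Six go to treatment terms (nicotine, flavor, their interaction, and each of these by cigarette group), leaving 354. Adding three position terms leaves 351. The nine-column design had full rank in every simulated allocation.

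**Bias.** Over the 24 orders each condition is equally often in each position, so common drift cancels from the contrasts. In simulation (2,000 trials per setting, 60 per group, orders in sets of 24), mean estimates were within 0.02 puffs of the truth with and without position.

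**Standard error.** Centered positions are −1.5, −0.5, 0.5 and 1.5, with sum of squares 2.25 + 0.25 + 0.25 + 2.25 = 5. Drift therefore adds 5s² to each person's within-person sum of squares on 3 degrees of freedom:

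residual variance without position ≈ SD² + (5/3)s²

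An e-cig main effect compares the mean of two sessions with the mean of two others, so its variance per person is SD²(1/2 + 1/2) = SD², and SE = √(variance/120). With SD 4 and position in the model, SE = √(16/120) = 0.365.

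**Power for a 1-puff effect.** The true sampling SD of the estimate stays near 0.365, because the design balances position. Power is then about Φ((1 − 1.967 × model SE)/0.365), where 1.967 is the t critical value.

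| Drift s | Residual variance without position | SE without | Excess over 0.365 | Power without | Power with |
|---|---|---|---|---|---|
| 0.25 | 16.10 | 0.366 | 0.3% | 78% | 78% |
| 0.5 | 16.42 | 0.370 | 1.3% | 77% | 78% |
| 1 | 17.67 | 0.384 | 5.1% | 75% | 78% |
| 2 | 22.67 | 0.435 | 19% | 65% | 78% |

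The simulation gave mean model SEs without and with position of 0.369 and 0.365 (s = 0.5), 0.384 and 0.365 (s = 1), and 0.436 and 0.366 (s = 2). Simulated power was 78.0% against 79.4%, 73.6% against 76.1%, and 67.0% against 79.8%, with simulation error of about 1 point each. Power with position does not depend on common drift, so the spread among those three values is noise around 78%. At s = 2, rejection under the null was 2.1% without position and 4.9% with it.

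For drifts of 0.5, 1 and 2, the SE excess is 2.3%, 8.9% and 32% at SD 3, and 0.8%, 3.3% and 12.5% at SD 5.

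**Interactions.** The cigarette-by-nicotine interaction has SE √(16/60 + 16/60) = 0.730, twice that of the main effect. A 2-puff interaction therefore has the same power as the 1-puff main effect in the table.

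**At the planned effect.** If effect size 0.5 is read as a paired difference, it is 2 puffs at SD 4. At s = 2, power is 99.98% with position and 99.91% without.

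**Cost with no drift.** Over 3,000 simulated allocations (two full sets plus 12 further orders per group), adding position raised the SE by 0.043% on average and by 0.27% at most.

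**Robust errors do not rescue it.** Under drift a person's own contrast is shifted by 2s, s, 0, 0, −s or −2s with equal chance, which has variance (4 + 1 + 1 + 4)s²/6 = (5/3)s². A sandwich SE absorbs the same excess. In simulation at s = 2 it was 0.431 without position and 0.359 with it.

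**Carryover is a separate matter.** An 18 mg/ml session follows another 18 mg/ml session in 1/4 of cases and a 3 mg/ml session in 1/2; for a 3 mg/ml session these fractions are reversed. Carryover that differs by Δ between concentrations thus shifts the nicotine contrast by (1/4 − 1/2)Δ = −Δ/4, with or without position. Equal carryover shifts nothing.

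**The case against.** The strongest reply is that nothing in the plan is invalid. The sentence in 3.1 follows directly on the remark that each arrangement occurs two or three times, so it most naturally concerns whole sequences, and on that reading it is right. Its second half, on bias, is right as well. The wide standard errors are conservative, and at the planned effect size power is above 99% either way. The loss appears for a 1-puff effect, which is half of one choice, and the study was not sized for that.

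The larger figures also need a drift of 2 puffs per session. That is 6 puffs, or 3 of 10 choices, between sessions 2 and 5, in the same direction for everyone, and nothing in the documents suggests it. Limited vaping experience bears more on e-cig puffs than on cigarette puffs. Position also removes only the shared part of drift. If individual slopes vary with an assumed SD of 2 puffs per session, the residual variance rises by (5/3) × 4 = 6.67. The excess at a drift of 1 then falls from 5.1% to √(24.33/22.67) − 1 = 3.6%, and at a drift of 2 from 19% to √(29.33/22.67) − 1 = 14%.

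All of this stands as a limit on the size of the gain, and it is why the point is one of precision and not validity. It does not remove the case for the change. The SAP states e-cig power only for the two main effects, while the study also asks how e-cig characteristics modify the effect of VLNC cigarettes. Those interactions have twice the standard error and much less power to spare.

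**Conclusion.** The concern holds. Position is absent from the models, it is estimable, common drift leaves the e-cig contrasts unbiased, and leaving position out makes their standard errors too wide. There is no inflation of false positives, and the VLNC versus NNC main effect is essentially untouched, because every completer contributes all four positions.

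The size depends on the ratio of drift per session to within-person SD, which the documents do not give. The excess in SE is under 1% at a ratio of 0.1, about 5% at 0.25 and about 19% at 0.5. These figures assume linear drift shared by all participants, complete data and the SAP's own linear model for a 0 to 20 outcome. The likely benefit is modest, but the cost is close to zero, so the change should be made.

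**What to change.** Add session position (2, 3, 4, 5) as a categorical fixed effect to the mixed models in SAP 6.3.1 and 6.4, and carry it into the GEE and negative binomial versions so that they remain comparable. In 3.1, replace the sentence on order with: *Effects of the 24 whole sequences will not be evaluated; session position will be adjusted for in the mixed models.*

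As an optional sensitivity analysis only, add the previous session's e-cig condition. Session 2 would be coded as having no e-cig predecessor, since the session 1 choice task has no e-cig and the later practice and flavor sampling use 0 mg/ml. This model raises the SE by about 5% (0.365 to 0.383 at SD 4), so it should not be primary. The gap between sessions, overnight abstinence and the CO check already make pharmacological carryover less likely.

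The cost is SAP wording, 3 of 354 residual degrees of freedom, and about 0.04% in standard error if there is no drift. No new data are needed. As the SAP is marked final, the change should be made as a dated amendment.

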3.2. Sample Size

Very little has been reported in the literature on the effect of VLNC cigarettes or the dual use of e-cigarettes on adolescent smokers. To determine a reasonable effect size (ES=mean diff/common SD) for sample size calculations, we considered several recent studies investigating alternatives to usual brand cigarettes in adolescents and young adults. In the first project of the CENIC 1 center grant, cigarettes per day (CPD) at weeks 2 and 6 were recorded for adult smokers using cigarettes with the same level of nicotine planned for our current project (15.8 mg/g vs 0.4 mg/g). (Donny et al., 2015) Selecting out the youngest participants (18-24 years of age), the comparison between these two nicotine groups resulted in an ES of 0.76 at 2 weeks and 0.85 at 6 weeks. A recent study of adolescent smokers (Cassidy et al., 2015) used a very similar design as the current proposal. Participants made a series of 20 choices between puffs of their usual brand cigarettes or money, where the amount of money varied over three sessions assigned to each subject in random order (\$0.00, \$0.10, \$0.50). The ES for the comparison between 10 and 50 cents was 0.73. Therefore, based on these previous studies, we determined that 60 subjects per cigarette group would allow for the detection of an ES of 0.60 or higher with minimum statistical power of 90% for a two-sided, two-sample test where the significance level is 0.05. For the within subject comparisons defined by the 2 factors for the e-cig characteristics, an ES of 0.5 or more for the two main effects would have at least 97% power in a repeated measures analysis if the sample size is 60 per cigarette group with a significance level of 0.05. Study enrollment will continue until the number of subjects completing all 5 sessions reaches 60 in each group (120 total). Sample size and power calculations were carried out using PASS 13 (NCSS, LLC. Kaysville, Utah, 2014).

4. Study Populations

